**Treatment Arms and Planned Duration for an Individual Subject:**

Subjects will participate in: a screening period of up to 27 days; 3 treatment periods, each of either 4 days (Period 1) or 3 days (Periods 2 and 3) duration; and a follow-up period of up to 10 days. The total study duration for each subject will be up to 47 days.

Cohorts 1 and 3: Subjects will receive a single dose of 50 mg lasmiditan or placebo in Period 1, 100 mg lasmiditan or placebo in Period 2, and 200 mg lasmiditan or placebo in Period 3.

Cohort 2: Subjects will receive single dose of 50, 100, or 200 mg lasmiditan or placebo in Period 1, 400 mg lasmiditan or placebo in Period 2, and 2 doses of 200 mg lasmiditan or 2 doses of placebo administered 2 hours apart in Period 3.

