## 5.4. Scientific Rationale for Study Design

A subject- and investigator-blinded, randomized, and placebo-controlled design has been chosen to minimize bias in the primary objective of this study, and a crossover design has been chosen to minimize the number of subjects required for the study. The study design that has been chosen is considered to be the most feasible to execute operationally. As this will be the first time that the commercial formulation of lasmiditan will be administered to humans, Caucasian

subjects have been included to allow comparisons between Japanese and Caucasian subjects to be made.

Single and repeated doses (2 single doses administered 2 hours apart) of 50, 100, and 200 mg lasmiditan are considered the planned clinical doses. Additionally, a supratherapeutic dose of 400 mg lasmiditan has been included for the assessment of QT interval. As patients currently receiving approved therapies for migraine may administer an additional dose 2 hours following their initial dose if symptoms do not alleviate, this study will also evaluate the safety, tolerability, and PK of 2 doses of 200 mg lasmiditan administered 2 hours apart.

Pharmacokinetic sampling time points have been selected to generate PK profiles sufficient to fulfill the study objectives.

Conducting the study in healthy subjects mitigates the potential confounding effects of the disease state and concomitant medications in patients. Healthy subjects are frequently used in the assessment of bioavailability of both small and large molecules. Conducting this study in Japanese subjects will support their inclusion in future studies with lasmiditan, and inclusion of Caucasian subjects enables the direct comparison between Japanese and Caucasian subjects.

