## **5.5. Justification for Dose**

Oral doses of 50, 100, and 200 mg lasmiditan are envisaged to be clinically effective doses, based on data obtained from previous completed studies. A supratherapeutic dose of 400 mg lasmiditan is being investigated to obtain additional PK data and to investigate any effects of lasmiditan on QT interval in Japanese subjects.

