9.4.5 Electrocardiogram (ECG)

The ECG data will be obtained directly from the 12-lead ECG traces. These data include the PR and QT intervals, QRS duration and heart rate. In addition, QTcF (the QT interval corrected using Fridericia's formula) will be calculated as follows:

$$QTcF = \frac{QT}{\sqrt[3]{(60/HR)}}$$

The ECG data will be listed and summarized by population and treatment, together with changes from baseline, where baseline is defined as the mean of the average values of the triplicate assessments collected at -1 hour, -0.5 hours, and predose on Period 1. All other time points are considered as post baseline, including predose on Periods 2 and 3.

Figures of mean ECG data and mean changes from baseline will be presented by population and treatment. The frequency of subjects with a maximum increase from baseline in QTcF interval will be summarized by population and treatment according to the following categories: >30 ms and >60 ms. In addition, the frequency of subjects with QTcF postdose values, according to the following categories: >450 ms, >480 ms and >500 ms, will be summarized by population and treatment.

The relationship between concentrations of lasmiditan and changes from baseline QTcF (Δ QTcF) will be explored graphically, using different symbols and colours for each group. The comparisons to be explored are:

- Japanese vs Caucasian
- Japanese (Male vs Female)
- Caucasian (Male vs Female)

A linear mixed-effects model will be fitted with the change from baseline in QTcF (Δ QTcF) as the response, the time-matched concentration as a covariate, population or sex and time-matched concentration-by-population (or sex) as fixed effects for the population or sex analysis respectively, and subject as a random effect. Population and sex will be fitted as binary variables, as appropriate (0=Caucasian, 1=Japanese, 0=Male, 1=Female accordingly). The intercept, slope, and random effect covariance from the model along with their 90% CI will be reported. If the model fails to converge, alternative models will be tested. A scatter plot of Δ QTcF versus the concentrations with the fitted lines will also be plotted. Additional analysis may be performed, if deemed necessary.

Example SAS Code:

```
proc mixed data=ecg alpha=0.1;
  class usubjid effect;
  model chg_qtcf = conc + effect + conc*effect / alpha=0.1 cl solution
  residual ddfm=bw;
  random intercept conc / subject=usubjid type=un s;
run;
```

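### The Japanese-Caucasian concentration-QTcF slope comparison covers different dose ranges; a matched-dose run and a linearity check should be prespecified beside it

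*SAP*

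**What the plan says.** SAP 9.4.5 lists Japanese versus Caucasian as the first concentration-QTcF comparison. The linear mixed model includes "time-matched concentration-by-population (or sex) as fixed effects for the population or sex analysis respectively", and the example code is "model chg_qtcf = conc + effect + conc*effect / alpha=0.1 cl solution", with a random intercept and slope per subject. On output it states: "The intercept, slope, and random effect covariance from the model along with their 90% CI will be reported". The section places no restriction on dose, cohort, period or concentration. The only stated trigger for a different model is non-convergence: "If the model fails to converge, alternative models will be tested".

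The populations do not receive the same doses. The Protocol synopsis says "Cohorts 1 and 3: Subjects will receive a single dose of 50 mg lasmiditan or placebo in Period 1", rising to 100 mg and 200 mg in Periods 2 and 3. Cohort 2, which is Japanese, goes on to "400 mg lasmiditan or placebo in Period 2, and 2 doses of 200 mg lasmiditan or 2 doses of placebo administered 2 hours apart". The high dose is deliberate: Protocol 5.5 includes 400 mg "to investigate any effects of lasmiditan on QT interval in Japanese subjects". Protocol 5.4 also says that "inclusion of Caucasian subjects enables the direct comparison between Japanese and Caucasian subjects".

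For the PK power model, SAP 9.3.2 names each population's dose range and drops Cohort 2 Period 3. SAP 9.4.5 has no equivalent.

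**The concern.** A straight line fitted to a curved relationship estimates an average gradient over whatever concentrations were observed. The Japanese average runs to about twice the Caucasian peak. If both populations follow the same flattening curve, the Japanese slope comes out lower and could be taken for reduced sensitivity. If both share an effect that appears only above the 200 mg peak, only the Japanese slope is positive and it could be taken for an ethnic QT signal. Because the slope difference is itself the comparison, a reader of the report could not separate population from dose range. No linearity criterion or common-range analysis is prespecified to help.

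**Working it through.** **1. Planned numbers (Protocol 5.2, SAP 7).** At 2 per sequence: Japanese (3 + 4) x 2 = 14; Caucasian 4 x 2 = 8. Both match the plan.

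**2. Active periods (SAP Tables 1-3, 2 per sequence).**

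| Dose | Japanese | Caucasian |
|---|---|---|
| 50 mg | 4 + 2 = 6 | 6 |
| 100 mg | 4 + 2 = 6 | 6 |
| 200 mg | 4 + 2 = 6 | 6 |
| 400 mg | 6 | 0 |
| 2 x 200 mg | 6 | 0 |
| Total | 30 | 18 |

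Periods without a Caucasian counterpart: 12/30 = 40%. On 50-200 mg single doses the sets balance exactly, 18 against 18.

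**3. Leverage of the high doses.** Inputs from Protocol 3.2: half-life about 4 h, tmax 1.5 to 2.5 h, approximately dose-linear PK. Times from Protocol 2: the 12 postdose ECG times from 1 to 48 h. Assumed: a one-compartment oral profile, C(t) proportional to exp(-ke t) - exp(-ka t), with ke = ln2/4 and ka solved from ln(ka/ke)/(ka - ke) = tmax. The 200 mg Cmax is set to 1, exposure does not vary between subjects, and placebo periods are left out.

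- Peaks: 400 mg = 2.0; 2 x 200 mg = 1.82 at the scheduled times (tmax 2 h).
- Sum of squares, sum of (C - mean C)^2, at tmax 2 h: Japanese 138.9, Caucasian 21.6.
- Share of the Japanese sum from 400 mg and 2 x 200 mg periods: 72-73% across the tmax range.
- Half of the observations in those periods still lie within the typical Caucasian range. Observations above it are 20% of Japanese active-period observations and about 62% of the sum of squares.

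**4. Effect on the slopes.** One identical curve in both populations, E = C/(C + EC50), with EC50 assumed as a multiple of the 200 mg Cmax. Least-squares slopes:

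| EC50 | Japanese/Caucasian slope ratio |
|---|---|
| 0.5 | 0.60-0.61 |
| 1 | 0.68-0.69 |
| 2 | 0.77-0.78 |
| 4 | 0.85-0.86 |
| linear | 1.00 |

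With matched doses every ratio is 1.00. With an assumed threshold curve, max(C - 1, 0), the Caucasian slope is 0 and the Japanese slope 0.39-0.41.

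The SAP fits random slopes, which give more weight to Cohort 1. With an assumed between-subject slope SD of 2 to 5, the EC50 = 0.5 ratio moves from 0.61 to 0.66-0.70, so least squares is near the worst case.

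**5. Dependence on effect size.** The artefact scales with the drug effect. Assumed: residual SD 6 ms, subject SD 3 ms, slope SD 0.5, EC50 0.5 to 4. The share of cases in which the 90% CI for the slope difference excludes 0 (nominal 10%) is:

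- 5 ms at the 200 mg Cmax: 14-38%
- 2 ms: 11-15%
- 1 ms: 10-11%

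A second set of simulations (2000 per curve) used the same SDs, included placebo periods, set a between-subject exposure SD of 0.35 on the log scale, and used saturable and quadratic curves, all 5 ms at that Cmax:

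| Fit | 90% CI excludes 0, curved shapes | Mean slope difference (ms per 200 mg Cmax) |
|---|---|---|
| All doses | 24-61% | -1.75 to +2.47 |
| 50-200 mg single doses only | 12-15% | -0.11 to +0.23 |
| All doses, shared quadratic term | 10-11% | -0.25 to +0.02 |

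Under linearity the all-dose fit gave 10%.

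**6. Price of matching.** Ratio of standard errors for the slope difference, residual error only: sqrt[(1/21.6 + 1/21.6) / (1/138.9 + 1/21.6)] = sqrt(0.0926/0.0535) = 1.32. The simulations gave 1.52/1.18 = 1.29. The all-dose quadratic fit gave 1.26.

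**The case against.** The strongest objection is that the bias needs both a QT effect and a curvature, and the documents report neither. Protocol 3.3 states that there was no significant QT prolongation at 100 or 400 mg. That does not establish linearity or a zero effect, but it is the only QT evidence given, and step 5 shows that the artefact nearly vanishes at 1-2 ms. This stands, and it limits the point.

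The plan is also not without a matched-dose view. SAP 9.4.5 summarizes and plots QTcF and its change from baseline by population and treatment, so 50, 100 and 200 mg can be compared descriptively. It plans a scatter plot with fitted lines, requests residuals in the code, and leaves room for additional analysis. This stands too. What is missing is narrower: a stated linearity criterion and a matched-range version of the slope contrast.

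The comparison is exploratory and unpowered, has no decision rule, and SAP 9.4.9 plans no inferential analyses. That lowers the priority, but the slopes and their intervals will still be reported.

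A reader might infer that the slopes are comparable only under exact linearity, or that the all-dose contrast should be replaced. Neither follows. Approximate linearity leaves a small bias. Restriction discards 40% of Japanese active periods and leaves two Cohort 2 subjects with no active period. It also matches doses, not concentrations.

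**Conclusion.** The dose-range mismatch is confirmed from the documents: 12 of 30 Japanese active periods against 0 of 18 Caucasian lie above the single 200 mg dose, and SAP 9.4.5 does not address it. The consequence is conditional. If the shared relationship is materially non-linear, the interaction term partly measures dose range, with a least-squares slope ratio of about 0.60-0.86 under the assumed saturable curves and somewhat closer to 1 under the SAP's random slopes. If the relationship is linear there is no bias, and if the effect is small the bias is negligible in milliseconds. The curves, variances and one-compartment profile are assumptions, so these sizes are illustrative.

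A reader might go further and infer that any reported population difference will be an artefact, or that the QT assessment of 400 mg in Japanese subjects is compromised. The documents do not support either. They give no evidence of curvature, and the all-dose slope in Japanese subjects does not depend on the Caucasian range. Giving 400 mg to Japanese subjects only is intended. The gap is in how the population contrast is to be read, and it is worth closing because doing so is cheap.

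**What to change.** In SAP 9.4.5, keep the planned all-dose model and prespecify two additions:

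- **(a) Matched-dose fit.** Run the same model on the single-dose 50-200 mg periods given in both populations: Cohort 1, Cohort 3 and Cohort 2 Period 1, 18 active periods each. Report its slope difference with 90% CI beside the all-dose contrast.
- **(b) Linearity check.** For example, add a shared quadratic concentration term to the all-dose model.

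Then state the reading rule. An all-dose slope difference is interpreted as a population difference only if it is also seen in the matched-dose fit or remains after the quadratic term. Label the all-dose contrast as extending beyond the Caucasian range.

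The cost is SAP wording, one run of the existing code on a subset, and the added term for the check. No new data are needed and dosing is unchanged. The downside is a wider interval for the matched-dose contrast, with a standard error up to about 32% larger. The planned all-dose estimate keeps its precision because it stays in the report.

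### Concentration-QTcF model (SAP 9.4.5): text and example code imply different reference groups, and, as a separate gap, no predicted QTcF change with a 90% CI is prespecified at the 400 mg or 2 x 200 mg peak

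*SAP*

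**What the plan says.** The text of SAP 9.4.5 describes a linear mixed model for change in QTcF, with time-matched concentration, population (or sex) and their interaction as fixed effects. On coding it says "Population and sex will be fitted as binary variables, as appropriate (0=Caucasian, 1=Japanese, 0=Male, 1=Female accordingly".

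The example SAS code has "class usubjid effect" and "model chg_qtcf = conc + effect + conc*effect / alpha=0.1 cl solution". It has no REF= or ORDER= option and no ESTIMATE, LSMEANS or prediction statement. SAP Section 14 records that Version 2 changed this code to let the slope differ between groups.

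The reporting sentence is "The intercept, slope, and random effect covariance from the model along with their 90% CI will be reported". It names no group and uses the singular, although the interaction model has two intercepts and two slopes. A scatter plot of change in QTcF "versus the concentrations with the fitted lines will also be plotted"; no confidence band is mentioned. On the descriptive side, "The ECG data will be listed and summarized by population and treatment, together with changes from baseline", and there are tables for increases above 30 and 60 ms and for values above 450, 480 and 500 ms.

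Protocol 5.4 explains that "a supratherapeutic dose of 400 mg lasmiditan has been included for the assessment of QT interval". Protocol 5.5 gives the purpose as "to investigate any effects of lasmiditan on QT interval in Japanese subjects". Protocol 10.3.1.2 leaves the detailed QT analysis to the SAP.

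**The concern.** A programmer who follows the text and one who follows the code get the same fit but different printed tables. The rows labelled intercept and concentration describe Caucasians in one table and Japanese in the other, and the interaction has the opposite sign. Nothing in the fit statistics would reveal that a table was read with the wrong coding. A slope could be credited to the wrong population, or a population difference reported in the wrong direction.

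The second issue does not depend on the first. A slope is not an effect in milliseconds. The supratherapeutic dose was added for QT, so the natural model summary is the predicted change, with its uncertainty, at the exposure that dose produces. The SAP names no concentration at which this is to be estimated.

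**Working it through.** The documents give no power, variance or effect figure for this model, so there is no plan figure to reproduce. The text's 90% CI does agree with alpha=0.1 in the code.

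**Step 1: which group the printed rows describe.**
- Text, numeric g = 0 or 1: E(y) = b0 + b1·conc + b2·g + b3·conc·g. The intercept and concentration rows are those of level 0, and b3 = slope(1) − slope(0).
- Code, CLASS with the last level set to zero: the same rows are those of the last level, and the interaction row is slope(other) − slope(last).
- The last level for population is Japanese, whether stored as 0/1 or as text. For sex it is Female if stored as 0/1, but Male if stored as text (Female sorts before Male).

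**Step 2: numerical check.** One trial was simulated with the SAP's sequences at 2 subjects each: (3 + 4) × 2 = 14 Japanese and 4 × 2 = 8 Caucasian. Post-dose ECG times came from the Schedule of Activities. Placebo periods were left out because Protocol 9.5.1 plans no assay of those samples. Assumed values: between-subject SD 5 ms, residual SD 6 ms, concentration in units of the mean 100 mg peak. The 400 mg peak is then 4 units, using the approximate dose linearity in Protocol 3.2. The SAP model was fitted with each reference level:

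| | Level 0 reference (text) | Level 1 reference (code) |
|---|---|---|
| Intercept (SE) | 2.416 (1.686), Caucasian | −2.970 (1.278), Japanese |
| Concentration slope (SE) | 1.783 (0.583), Caucasian | 1.123 (0.289), Japanese |
| Group term | −5.386 | 5.386 |
| Interaction (SE) | −0.660 (0.651) | 0.660 (0.651) |
| Log-likelihood | −1850.3542 | −1850.3542 |
| Japanese prediction at 400 mg peak | 1.52 ms | 1.52 ms |

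The columns agree: 2.416 − 5.386 = −2.970 and 1.783 − 0.660 = 1.123. Only the labelling moves.

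**Step 3: the other group's slope.** Under the text's coding the Japanese slope is a sum of two rows with no printed CI. Under the code this is so for the Caucasian slope. The two groups share no subjects, so the missing SE can be recovered by hand if the interaction row is also reported: √(0.651² − 0.289²) = 0.583, as in the other column. The reporting sentence does not list that row.

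**Step 4: the prediction at the 400 mg peak, Japanese.**
- Point estimate: −2.970 + 4 × 1.123 = 1.52 ms, available from the reported coefficients.
- Variance: SE(a)² + C²·SE(b)² + 2·C·ρ·SE(a)·SE(b), where ρ is the correlation of the two fixed-effect estimates. The SAP does not report ρ. The random-effect covariance it does report measures between-subject variation and cannot stand in for it.
- With the fitted ρ = −0.079: √(1.278² + 16 × 0.289² − 8 × 0.079 × 1.278 × 0.289) = 1.65, so the 90% CI is 1.52 ± 1.645 × 1.65 = −1.20 to 4.24 ms.
- With ρ unknown, from −1 to +1: the SE runs from 0.12 to 2.43 and the upper limit from 1.72 to 5.53 ms.

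**Step 5: what else covers 400 mg.** The by-treatment summaries give observed changes at 400 mg. The statistics in SAP 9.1 are mean, SD, median, minimum, maximum and N, with no CI. Three of the four Cohort 2 sequences include 400 mg, so about 3 × 2 = 6 subjects contribute, while the model draws on all Japanese subjects.

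**The case against.** The strongest reply is that little is at risk. The analysis is exploratory: QT is not among the objectives or endpoints, and SAP 9.4.9 plans no inferential safety analysis. The code is headed as an example, and a careful reader of the SOLUTION table sees which level is set to zero. If the code is followed, the Japanese intercept and slope are printed directly with CIs, and those belong to the only population given 400 mg. SAP 9.4.5 also leaves room for additional analysis. All of this stands and limits the weight of the point. It does not make text and code agree, and an open clause does not prespecify an estimate.

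Stronger readings are tempting and are not supported:

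- **That the coding mismatch is why there is no 400 mg effect.** It is not. Predictions are identical under both codings.
- **That no QTcF effect at 400 mg will be available.** Observed changes are summarized by treatment, fitted lines are plotted, and a point estimate follows from the coefficients. Only the prespecified model estimate with its CI is missing.
- **That the reference is swapped in all three fits.** The text never calls level 0 the reference; a numeric 0/1 variable implies it. If sex is stored as text, Male is the CLASS reference and neither sex fit is swapped.
- **That the prediction should be the main QT result.** The model has no placebo term, so intercept plus slope times concentration is a change from the Period 1 baseline and not a placebo-corrected drug effect. Promoting it above the planned outputs would be a preference.

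**Conclusion.** The point holds as two modest, separate weaknesses in an exploratory analysis.

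1. Text and code imply different parameterizations. The consequence is possible mislabelling of the intercept and slope and a reversed interaction sign. It is clear for the population fit and depends on data storage for the two sex fits. No fit or prediction changes.
2. No model-predicted change in QTcF with a 90% CI is prespecified at the 400 mg or 2 x 200 mg peak, although QT assessment is a stated reason for the 400 mg dose. That CI cannot be built from the quantities the SAP says it will report.

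The first item rests on SAS default level ordering, which the documents do not describe. The millisecond figures come from assumed variances and one simulated data set, with normal quantiles. They show that the missing correlation can matter and do not forecast this trial's result.

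**What to change.** In SAP 9.4.5:

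- Make text and code agree. Either take `effect` out of CLASS and fit it as numeric 0/1, or write `effect(ref='0')` and state the reference level in the text.
- Reword the reporting sentence so that it names the group for each intercept and slope.
- Add ESTIMATE statements with 90% CIs for each group's own slope, and for the slope difference in a stated direction (Japanese minus Caucasian, Female minus Male).
- Add ESTIMATE statements with 90% CIs for the predicted change in QTcF at the observed geometric mean Cmax of each dose given to that group. For Japanese subjects this includes 400 mg and 2 x 200 mg.
- Label the prediction as a change from the Period 1 baseline that is not placebo-corrected, and show it alongside the planned outputs.

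The cost is a few lines of code and one table from a model already planned. Data collection and trial conduct do not change.

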## **7.2. *Method of Treatment Assignment***

Japanese subjects will be enrolled in Cohort 1 or 2, and Caucasian subjects will be enrolled into Cohort 3.

Within each cohort, subjects will be randomized to a treatment sequence using a computer-generated allocation schedule. There will be no randomization between cohorts. Randomization will be stratified by sex, such that there will be an approximately equal number of male and female subjects in each cohort.

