### **7.2.1. *Selection and Timing of Doses***

The doses will be administered at approximately the same times on each day.

The actual time of all dose administrations will be recorded in the subject's electronic case report form (eCRF).

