#### 9.5.1. Bioanalysis

Samples will be analyzed at a laboratory approved by the sponsor and stored at a facility designated by the sponsor.

Concentrations of lasmiditan and metabolites M7, M8, (S,R)-M18, and (S,S)-M18 will be assayed using a validated liquid chromatography with tandem mass spectrometry method. Analyses of samples collected from placebo-treated subjects are not planned.

Bioanalytical samples collected to measure investigational product concentrations will be retained for a maximum of 2 years following last subject visit for the study. During this time, samples remaining after the bioanalyses may be used for exploratory analyses such as metabolism and/or protein binding work.

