- AUC parameters will be calculated using a combination of the linear and logarithmic trapezoidal methods (linear-log trapezoidal rule). The linear trapezoidal method will be applied up to t_{\max} and then the logarithmic trapezoidal method will be used after t_{\max} . The minimum requirement for the calculation of AUC will be the inclusion of at least three consecutive plasma concentrations above the lower limit of quantification (LLOQ), with at least one of these concentrations following C_{\max} .
- AUC($0-\infty$) values where the percentage of the total area extrapolated is more than 20% will be flagged. Any AUC($0-\infty$) value excluded from summary statistics will be noted in the footnote of the summary table.
- Half-life ($t_{1/2}$) will be calculated, when appropriate, based on the apparent terminal log-linear portion of the concentration-time curve. The start of the terminal elimination

phase for each subject will be defined by visual inspection and generally will be the first point at which there is no systematic deviation from the log-linear decline in plasma concentrations. Half-life will only be calculated when a reliable estimate for this parameter can be obtained comprising of at least 3 data points. If $t_{1/2}$ is estimated over a time window of less than 2 half-lives, the values will be flagged in the data listings. Any $t_{1/2}$ value excluded from summary statistics will be documented in the footnote of the summary table.

- A uniform weighting scheme will be used in the regression analysis of the terminal log-linear portion of the concentration-time curve.
- The parameters based on last predicted quantifiable drug concentration (C_{last}) will be reported.

Individual PK Parameter Rules

- Only quantifiable concentrations will be used to calculate PK parameters with the exception of special handling of certain concentrations reported below the lower limit of quantitation (BQL). Plasma concentrations reported as BQL will be set to a value of zero when all of the following conditions are met:
 - The compound is non-endogenous.
 - The samples are from the initial dose period for a subject or from a subsequent dose period following a suitable wash-out period.
 - The time points occur before the first quantifiable concentration.
- All other BQL concentrations that do not meet the above criteria will be set to missing.

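### The concentration-QTcF model has no time or period term, so period drift or a daily rhythm aligned with concentration can bias its slopes and the Japanese-Caucasian slope difference

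*SAP*

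**What the plan says.** SAP 9.4.5 contains the only planned model of concentration against QTcF. The example code is "model chg_qtcf = conc + effect + conc*effect / alpha=0.1 cl solution", with an unstructured random intercept and concentration slope per subject and 90% intervals. The prose agrees: it names the concentration covariate, population or sex, and then "time-matched concentration-by-population (or sex) as fixed effects for the population or sex analysis respectively, and subject as a random effect". Neither has a nominal-time, period or treatment term, so this is not a coding slip. The section allows other models if the fit fails to converge and further analysis if needed, but neither clause prespecifies an adjustment.

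Baseline is the mean of three Period 1 pre-dose assessments. Of the rest, the section says "All other time points are considered as post baseline, including predose on Periods 2 and 3".

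On dosing, Protocol 7.2.1 says "The doses will be administered at approximately the same times on each day". The synopsis gives Cohorts 1 and 3 "a single dose of 50 mg lasmiditan or placebo in Period 1, 100 mg lasmiditan or placebo in Period 2", then 200 mg or placebo in Period 3. Cohort 2, which is Japanese only, moves from 50, 100 or 200 mg to 400 mg and then to 2 × 200 mg. Protocol 7.2 adds: "Randomization will be stratified by sex, such that there will be an approximately equal number of male and female subjects in each cohort".

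On placebo samples, Protocol 9.5.1 says "Analyses of samples collected from placebo-treated subjects are not planned". The SAP does not say what concentration, if any, placebo-period records take in this model.

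**The concern.** With a fixed dosing time, concentration partly tracks the clock. With ascending doses, it also tracks period. Because change is measured from Period 1 only, drift across periods stays in the response. A model whose only time-varying regressor is concentration must attribute shared change of either kind to concentration, to the extent that the two are correlated. The dose layouts differ between populations, so the false slope differs too, and it passes into the interaction.

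Protocol 10.3.1.2 leaves the detailed QT analysis to the SAP. Protocol 5.4 and 5.5 give QT assessment as a reason for the 400 mg dose. SAP section 14 records that version 2 changed this code so that slopes could differ by group, and that group difference is what the omission distorts.

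**Working it through.** **Plan's own figures.** At about 2 completers per sequence: 2 × (3 + 4) = 14 Japanese and 2 × 4 = 8 Caucasian, as SAP section 7 states. Each cohort has one placebo sequence per period, so placebo subject-periods are 3 cohorts × 2 subjects × 3 periods = 18 of 22 × 3 = 66.

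**Dose by period** (Protocol Tables LAIE.5.2 to 5.4; 2 × 200 mg counted as 400; means over active sequences).
- Caucasian: 50, 100, 200 mg. Each dose occurs in one period only.
- Japanese, Period 1: (50 + 50 + 50 + 100 + 200)/5 = 90 mg.
- Japanese, Period 2: (100 + 100 + 3 × 400)/5 = 280 mg.
- Japanese, Period 3: (200 + 200 + 3 × 400)/5 = 320 mg.

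**Records.** Matched ECG and PK times after baseline number 12 in Period 1 and 13 (with predose) in Periods 2 and 3. Total: 22 × 12 + 44 × 13 = 836. Active: 16 × 12 + 32 × 13 = 608.

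**Method.** Set the drug effect to zero and let *m* be a QTcF shift common to all subjects. The expected estimate is E(b) = (X'V⁻¹X)⁻¹X'V⁻¹m, with X as in the SAP model. From Protocol 3.2: half-life 4 h, tmax 2 h (within the 1.5 to 2.5 h given), dose-linear. Assumed, because the documents give none: one-compartment curve, exposure log-SD 0.3, residual SD 6 ms, between-subject SD 4 ms, and the shifts themselves.

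**Pencil check of direction.** For Caucasian peaks alone, regress shifts 0, 2, 4 ms on 50, 100, 200 mg (mean 116.7). The slope is (66.7 × 2 + 83.3 × 2)/(66.7² + 16.7² + 83.3²) = 300/11,667 = 0.0257 ms per mg, or 5.1 ms at 200 mg. Late, near-zero concentrations carry the same period shift and dilute this in the full fit.

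**Full fit, SAP model, placebo left out, ms at the 200 mg Cmax:**

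| Assumed shift | Caucasian | Japanese | Caucasian minus Japanese |
|---|---|---|---|
| Drift +2 ms per period | +2.0 to +2.1 | +0.7 | about +1.4 |
| 24 h cosine, amplitude 2.5 ms, peak 3 h postdose | +2.0 | +1.0 | +1.0 |
| Same, trough at 3 h | −2.0 | −1.0 | −1.0 |
| Same, peak 9 h | within about 0.2 of zero | within about 0.2 of zero | within about 0.2 of zero |

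The SE of the difference is about 1.3 to 1.35 ms. Bias is proportional to the assumed shift. Entering placebo at 0 without new terms still leaves +1.9 ms (Caucasian) and 1.2 ms (difference) for the drift.

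**Coverage of the 90% CIs** (REML, 600 replicates). With no shift, coverage is 92%. Drift gives 53% for the Caucasian slope, 64% for the Japanese slope and 80% for the difference. For the Japanese slope, the 3 h cosine gives 39% and the 9 h cosine 92%.

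**Window.** SAP 9.3.1 says "All other BQL concentrations that do not meet the above criteria will be set to missing", but that rule is written for PK parameters, and no LLOQ is given. Over 12, 24 or 48 h windows, the drift gives 2.0 to 3.7 ms for the Caucasian slope.

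**Sex contrasts.** With equal exposure, bias is close to 0. Protocol 3.2 reports 20% to 30% higher Cmax and 30% higher AUC in females. With 30% higher exposure, the shifts above give about 0.2 to 0.5 ms, against SEs of about 0.9 to 2.3 ms. A larger assumed within-day shift of 5 ms gives 0.62 ms (Japanese) and 1.09 ms (Caucasian), which is 40% and 70% of the 1.55 ms in the population contrast. The male and female slopes themselves carry the full bias.

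**With time and period terms and placebo at 0.** Shared shifts give bias 0.00 in the expectation, within 0.04 ms by simulation, and coverage of 91% to 92%.

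**If the shift is not shared.** With drift in Japanese subjects only, common terms raise the bias in the difference from about 0.7 to 1.5 ms and move the Caucasian slope from 0 to about −1.4 ms. With drift in Caucasian subjects only, the difference improves from about 2.0 to 1.6 ms. Population-specific terms remove both.

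**The case against.** The case for leaving the model alone is fair. The analysis is exploratory (Protocol 10.3.1.2), the study is unpowered (SAP section 7), SAP 9.4.9 plans no inference, and no decision threshold is attached to the slope. Protocol 3.3 reports no significant QT prolongation at 100 or 400 mg. Subjects are in-house under controlled conditions with triplicate supine ECGs, which limits stray change. ECG changes are summarised by treatment, placebo included, so shared drift would be visible. Every shift above is assumed, and the drift bias in the population difference is only about the size of its SE. All of this stands, and it lowers the weight. It does not correct the slope or its CI, which the SAP will report.

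A reader might infer more than the documents support:
- **That any time-of-day change biases the slopes, or that the CIs must under-cover.** A rhythm peaking at 9 h does almost nothing; alignment with the concentration curve is needed.
- **That the single Period 1 baseline is the fault.** A period term would absorb it.
- **That the sex contrasts are immune because randomisation is stratified by sex.** Stratification equalises the dose-period layout, not exposure.
- **That placebo periods will be discarded.** This is one reading; the SAP states no rule.

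**Conclusion.** The omission is certain, and the design gives it a route to matter. Period drift, or a rhythm aligned with concentration, can bias both slopes and the Japanese-Caucasian slope difference, up or down. Under the assumed drift or 3 h cosine, the false slopes are about 0.7 to 2.1 ms and the false difference about 1.0 to 1.4 ms at the 200 mg Cmax, with reduced CI coverage. The actual size is unknown because the documents give no drift, rhythm or variance. The sex contrasts are less affected, conditional on similar exposure. The point is worth correcting because the correction is cheap, but it ranks low among changes to make.

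**What to change.** In the prose and code of SAP 9.4.5, for both the population and sex models, add categorical nominal post-dose time and period. State that placebo-period records enter with concentration 0, and say how post-dose values below quantification enter this dataset.

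For the Japanese-Caucasian comparison, also prespecify and report a fit with time-by-population and period-by-population terms. This should not be optional, because common terms help only if the effects are shared. That is not assured: the longer fast of about 5 h applies only in Cohort 2 Period 3, Japanese meals may differ (Protocol 6.3.1), and Cohort 3 may be dosed independently of the other cohorts (Protocol 10.3.3).

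No new data are needed. The common terms add 12 + 2 = 14 fixed parameters. Under the assumed variances, they change the SE of the population difference to about 1.20 ms, from about 1.35 ms (placebo left out) or 1.15 to 1.19 ms (placebo at 0). Population-specific terms raise it to about 1.6 ms, roughly +20% to 25% and +35% to 40% on those two bases. In the Caucasian-only sex model, slope SEs rise by about 10% and 20% to 23% with the common terms. Adding the terms while leaving placebo out would raise the Japanese slope SE by 42% to 48%, so the placebo rule is what keeps the cost low.
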